#### **10.4.2. Sensitivity analyses**

To account for the participants' 'adjustment time' to wearing the activity belts, we will exclude the first day of wear-time from analyses.

We will be comparing the wear-time location data from parent-report measures to the data from the GPS logger to evaluate whether parent-report alone provides enough information on the participant's location information. We will assess the GPS data for each participant, specifically looking for substantial coordinate (latitude and longitude) changes. Any deviations from the home coordinates will be cross-referenced to the mother's report by comparing the coordinate's corresponding time stamp and the time indicated by the mother. We will also assess any coordinate changes if the parent indicated that the child left the home.

We will run the same model described in objective 2, however we will stratify by preschooler sex.

We will be comparing the mean cp15s of the Trost and colleagues cut-points to the cut-points established by Pate and colleagues, Sirard and colleagues, and Van Cauwenberge and colleagues. We will conduct an ANOVA to establish if there is a difference among strata listed above.

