## **10. Analysis**

### **10.1. Outcome measure**

The primary measure of physical activity will be a continuous variable that represents the average total physical activity level of each child, expressed as a mean counts per 15 seconds (cp15s) averaged over all of the child's eligible wear time on all days that meet criteria for inclusion.

Due to the young age of the participants, compliance for a full 7 days may prove to be difficult; therefore we will use 3 days of data as the minimum number of valid days per child. If a child has more than 7 days of eligible wear time, we will include all additional days with sufficient wear time.

Accelerometry data is collected at 30 Hz, meaning that data measures are collected 30 times per second. Activity counts collected within the 30 measures/second are averaged to provide an activity count for that particular second. We will be analyzing the data in sections of 15 seconds, therefore we will be averaging activity counts within 15 second intervals (average 15 data points of activity counts). These 15 second epochs (cp15s intervals that have been analyzed) will be used to analyze physical activity levels by categorizing them into sedentary behaviour (SED; sitting, laying down, etc.), light physical activity (LPA; walking, crawling, etc.), and moderate-to-vigorous physical activity (MVPA; running, jumping, etc.) using the cut-points chosen.

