We will use the cut-points established by Trost and colleagues:  $\leq 48$  cp15s for sedentary behaviour (SED), 49-418 cp15s for light physical activity (LPA), and  $>418$  cp15s for moderate-to-vigorous physical activity (MVPA) . These cut-points were chosen because they were derived from direct observation of a sample of toddler and preschool-aged children while wearing the ActiGraph GT1M accelerometer . Videos of the children playing were coded using a modified version of the Children's Activity Rating Scale before receiver operating characteristic curve analyses were conducted to determine the corresponding cut-points to the 3 categories of interest: SED, LPA, and MVPA . These results were found to exhibit excellent classification accuracy . They were then cross-validated against pre-existing cut-points that are established for toddlers and preschoolers, which were not found to be significantly different than the pre-established cut points established by Pate and colleagues  and those established by National Health and Nutrition Examination Survey .

We will then be able to calculate total time (minutes) as well as proportion of time (%) spent in each activity category (SED, LPA, MVPA). The overall mean cp15s for each child will be based on all 15-second epochs that occurred during eligible wear periods from the time that the caregiver indicated the child woke up until the time that the caregiver indicated the child went to sleep at. If this data is missing, we will use eligible wear periods between 8am to 8pm. This mean will exclude non-wear periods as defined above and when the accelerometer was not being worn by the child (based on daily logs collected from the caregivers via afternoon telephone call; Section 9.3.7.).

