For each child, we will calculate the mean number of minutes per day and the proportions of the child's total eligible wear time that are classified as SED, LPA and MVPA. We will also determine the proportion of days on which each child reached or exceeded 180 minutes of activity classified as LPA or MVPA, and the proportion of days on which each child reached or exceeded 60 minutes of activity classified as MVPA. These cut-offs are based on the Canadian preschooler physical activity guidelines established by Tremblay and colleagues , as there are no Bangladeshi standards available at present. If Bangladeshi guidelines are released before data analysis and reporting is completed, we will also apply those standards in our analyses.

For each child, we will establish the following parameters related to accelerometry:

- Total duration (minutes) of the potential data collection period on all days on which the accelerometer was instructed to be worn;
- Total eligible wear time (minutes), including data collected while the child was awake (from the time that their caregiver indicated that they woke up until the time that they went to sleep). If this data is not provided, total eligible wear time will be measured between 8am and 8pm. Non-wear periods will be excluded based on the following

criteria:  $\geq 20$  minutes of 0 cp15s allowing for up to 2 minutes of 0-100 cp15s in that period. A given day will be considered eligible for inclusion if there are at least 10 hours/day (600 min) between the indicated time period that the child was awake at, or between 8am to 8pm of wear time for those with missing data, after excluding non-wear periods;

- Total indoor eligible wear time (minutes; excluding non-wear periods as previously defined), based on maternal report;
- Total eligible wear time in or around the home (minutes; excluding non-wear periods as previously defined), based on combination of maternal report and GPS logging. "Around the home" will be defined as occurring in the same building or property of the home (e.g., rooftop, neighbouring apartment in the same building, common areas of the apartment building, private courtyard areas that are on the same property as the home in which the child resides).

For purposes of secondary and sensitivity analyses, we will also estimate for each child:

- Mean cp15s for indoor activity
- Mean cp15s for activity in or around the home

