- Mean cp15s on a day that is typically a work day (Sunday through Thursday)
- Mean cp15s on a Friday and/or Saturday (weekend)

For each of the above measures, we will also classify the activity in terms of average daily minutes and proportion of total time spent in SED state, LPA state, and MVPA state. In sensitivity analyses, we will compare the average daily minutes and proportion of total time spent in each activity category across different cut-off points that have been established by various research groups:

- Proportion of time spent in activity categories established by Pate and colleagues (SED:  $\leq 199$  cp15s; LPA: 200-419 cp15s; MVPA  $\geq 420$  cp15s)
- Proportion of time spent in activity categories established by Sirard and colleagues (SED:  $\leq 301$  cp15s; LPA: 302-614 cp15s; MVPA  $\geq 615$  cp15s) Proportion of time spent in activity categories established by Van Cauwenberge and colleagues (SED:  $\leq 372$  cp15s; LPA: 373-584 cp15s; MVPA  $\geq 585$  cp15s)

To address aim 4, we will analyze sleep quality and quantity directly on the nighttime accelerometry wear periods. Sleep data will be measured in 60-second epochs. This is obtained from the same accelerometry file that the activity data is derived from; however, data will be re-integrated into a 60-second epoch file (analyzes number of activity counts in every 60-second period).

Using the manufacturer's add-on to the ActiLife software (ActiLife 6 Full sleep Features Upgrade), we will be able to detect the number of sleep periods as well as the duration and quality of the sleep periods within the accelerometry file for each participant. The software will also detect and describe:

- Time in bed/out of bed (am/pm); duration in bed (hours; min)
- Sleep onset (when sleep commenced; am/pm)
- Total Sleep Time (TST; hours, min)
- Wake After Sleep Onset (WASO; describes how many minutes after sleep onset the participant woke up; min)
- Awakenings (number of awakenings during sleep onset)
- Average awakenings (average duration of awakenings during sleep onset; min)
- Total activity counts during sleep period (cp60s)
- Movement Index (MI)
- Fragmentation Index (FI)
- Sleep Fragmentation Index (SFI)
- Sleep Efficiency (%)

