To address our first objective, we will first create a histogram of the distribution of the data to assess the spread and shape of the frequency distribution of each of the categories of all of the physical activity data (average cp15s across all days for each participant). The number of bins within the histogram will be determined using the equation  $1 + 3.3\log_{10}(n)$ . A boxplot will then be created to assess the spread, as measured by the median; interquartile range (IQR); range of observations; presence of outliers; and provide additional information about the shape of the data. Finally, a Q-Q plot will be created to compare the frequency distribution of the data to a normal distribution. Using the shape and direction of the curvature, we will assess any deviation from normality.

We will estimate the mean and 95% confidence interval of cp15s for total physical activity of the sample of children, overall and stratified into the following groups:

- Boys and girls
- BMI categories (underweight, normal, overweight and obese)
- Household food security status (food secure, moderately food insecure; severely food insecure)
- Anemic and non-anemic

We will then summarize the distributions of the average amount (# of minutes) and proportions of wear time spent engaging in SED, LPA, and MVPA, over the measurement period.

Distributions of each time spent in each level of activity will be shown graphically (histograms, kernel density plots) and summarized using conventional descriptive statistics: mean and standard deviation if normally distributed, or median and interquartile range if not normally distributed.

We will then estimate the frequency of children who met Canadian physical activity recommendations on any day, and the average number of days on which children met the recommendations (180 minutes of activity classified as LPA or MVPA, working towards 60 minutes of activity classified as MVPA). Bangladeshi recommended guidelines for preschool-aged children will be used if they are released before statistical analyses begin. These data will be compared to published results in similar international, preschooler populations.

The above analyses will be repeated using data restricted to indoor wear time, in and around the household wear time, on weekdays, and on weekends.

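### The cut-point sensitivity analysis in section 10.4.2 compares mean cp15s, which no cut-point enters, and so conflicts with section 10.1, which names time in each activity category

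*Combined protocol and SAP*

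**What the plan says.** Section 10.1 makes the primary measure a continuous one, "expressed as a mean counts per 15 seconds (cp15s) averaged over all of the" child's eligible wear time. It adds: "The overall mean cp15s for each child will be based on all 15-second epochs that occurred during eligible wear periods". The cut-points come in afterwards. They sort epochs into sedentary behaviour (SED), light activity (LPA) and moderate-to-vigorous activity (MVPA), from which minutes and percentages are calculated.

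For sensitivity to the cut-points, section 10.1 says "we will compare the average daily minutes and proportion of total time spent in each activity category across different cut-off points", and it lists three alternative sets with their limits.

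Section 10.4.2 returns to the same four sets but names another outcome: "We will be comparing the mean cp15s of the" primary cut-points is to be set against the three alternatives. The next sentence is the test: "We will conduct an ANOVA to establish if there is a difference among strata listed above". The strata are not defined. The sentence just before lists the four cut-point sets. The only stratification named in section 10.4.2 itself is by sex: "We will run the same model described in objective 2, however we will stratify by preschooler sex". Section 10.4.1 has a further list of sex, BMI, food-security and anemia groups, introduced by "overall and stratified into the following groups".

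**The concern.** A sensitivity analysis should be able to give a different answer when the assumption under test is changed. Here the assumption is the cut-point set, and the outcome named in section 10.4.2 does not depend on it. An analyst who follows that section literally will find no difference between the sets and may report that the findings are robust to cut-point choice, although the data were never able to show otherwise.

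The results that do depend on the cut-points are the time in each category and the guideline results built on it (180 minutes of LPA or MVPA, 60 minutes of MVPA), which are part of Objective 1. Section 10.1 points the sensitivity analysis at category time and section 10.4.2 points it elsewhere, so the reader cannot tell which will be done. Neither section says how four values from the same child are to be compared.

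**Working it through.** **Inputs.** Definition of mean cp15s: section 10.1. Cut-points: section 10.1, as follows.

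| Set | SED | LPA | MVPA |
|---|---|---|---|
| Primary | ≤48 | 49–418 | >418 |
| Alternative A | ≤199 | 200–419 | ≥420 |
| Alternative B | ≤301 | 302–614 | ≥615 |
| Alternative C | ≤372 | 373–584 | ≥585 |

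Sample size 60 and SD 9.7 cp15s: section 9.6.

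**The plan's own figure.** Margin of error = 1.96 × 9.7 / √60 = 19.012 / 7.746 = 2.454, which reproduces the stated ±2.45. This figure concerns the overall mean cp15s. The plan gives no figure for the cut-point comparison.

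**Step 1: does a cut-point enter mean cp15s?** For one child with N eligible epochs, let S be the sum of counts within each category. Then

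mean cp15s = (S_SED + S_LPA + S_MVPA) / N = (sum of all counts) / N.

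Moving a limit moves epochs from one term to another and leaves the total and N unchanged. The only count threshold applied earlier is the 0–100 cp15s allowance in the non-wear rule. It is fixed and belongs to none of the four sets, so N is also the same under each.

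**Step 2: ANOVA across the four sets.** The four columns of 60 values are identical.
- Between-set sum of squares = 60 × Σ(set mean − grand mean)² = 0, on 3 degrees of freedom.
- Residual mean square, taking SD 9.7: 9.7² = 94.09, on 4 × 60 − 4 = 236 degrees of freedom.
- F = 0 / 94.09 = 0, p = 1. Any positive SD gives the same result.
- Within child, the set and residual sums of squares are both zero, so F = 0/0 and is undefined.

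A simulation of 60 children, each with 7 days of 600 minutes, agreed. The largest within-child difference between sets was 0.0, with F = 0 and p = 1, at assumed population means of 100, 150 and 200 cp15s.

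**Step 3: does the section 10.1 outcome respond?** The SED upper limit rises from 48 to 199, 301 and 372, so SED time cannot fall under any alternative set. How much it rises depends on the epoch distribution, which the documents do not give. For illustration only, the same simulation (zero-inflated gamma counts, an assumption) gave these minutes per day at a mean of 150 cp15s:

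| Set | SED | LPA | MVPA |
|---|---|---|---|
| Primary | 316 | 217 | 67 |
| Alternative A | 450 | 83 | 67 |
| Alternative B | 498 | 68 | 34 |
| Alternative C | 521 | 41 | 38 |

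Over assumed means from 100 to 200 cp15s, SED ran from 348 down to 298 under the primary set and from 559 down to 489 under alternative C. These sizes are not predictions. They show that category time moves with the set while mean cp15s stays fixed.

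**The case against.** **Section 10.4.2 may be a loosely worded pointer to section 10.1.** Section 10.1 lists several mean cp15s measures under "For purposes of secondary and sensitivity analyses, we will also estimate for each child" and then says each will also be classified into category time. That is plausible, and it answers a stronger reading that a reader might infer, namely that the plan contains no usable comparison between cut-point sets. The documents do not support that reading, because section 10.1 plans such a comparison on a suitable outcome. What remains is that section 10.4.2 names a different quantity and attaches a test to it.

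**Mean cp15s could mean the mean within each category.** The study summary leaves some room for this, and such a mean would respond to the cut-points: in the simulation at an assumed mean of 150, the mean within SED was about 6, 38, 58 and 70 across the four sets. The statement that the analysis is uninformative therefore applies to the overall mean cp15s. That is the better-supported reading, because no section defines a within-category mean, and such a mean would still differ from the section 10.1 outcome.

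**The strata could be subgroups.** An ANOVA of mean cp15s by sex, for example, would be a legitimate test of that difference. It would come out the same under every cut-point set, so it would say nothing about cut-points. The sentence order favours the four sets as the intended meaning, but the wording needs settling.

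**The matter is minor.** It concerns one sensitivity paragraph. This is right as to scope, and it limits the weight of the point. It does not remove the risk that a guaranteed null result is reported as robustness.

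**Conclusion.** The point holds for the overall mean cp15s as section 10.1 defines it. Compared across the four sets, it gives F = 0 and p = 1 (0/0 within child) by construction, with no assumption about the data beyond some variation between children. Sections 10.1 and 10.4.2 name different outcomes for the same analysis, and neither says how the four values from one child are compared.

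A reader might go further and infer that the main results are compromised. They are not: the overall mean cp15s, its ±2.45 precision and the Objective 2 and 3 models do not use the cut-points. How far category time will shift between sets cannot be stated from the documents, and the simulated minutes are illustrative. The plan should be corrected before analysis. The correction is one of alignment and leaves the design as it is.

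**What to change.** In section 10.4.2:

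1. Replace mean cp15s with the section 10.1 outcomes: minutes per day and percentage of wear time in SED, LPA and MVPA.
2. Replace the ANOVA, which if run one-way would treat the four sets as independent groups, with a within-child comparison of each alternative set against the primary set. Paired differences with a 95% CI would do, or median and IQR where the differences are not normal, in line with the summary rule in section 10.4.1. A repeated-measures analysis of category time would also serve.
3. State what the strata are. If subgroups are meant, compare category time between them under each set.

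The cost is a change to two sentences and slightly more tabulation. The data are already to be collected.

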### **11.Data Security and Protection of Subject Confidentiality**

Data will be entered and accessed using RedCap (Sick Kids version) with an encrypted laptop and managed on a secure server at the iccdr,b in Dhaka. This laptop will be accessed by the student investigator during the study collection period in Dhaka, and then transported back to Toronto when the student returns post-data collection period. If any data are collected after the student investigator returns to Toronto, data will be securely transferred to Toronto via a

secure web portal. All participants will be assigned a unique study ID number, which will be used to ensure that transferred data is de-identified.

All photographs will be organized, stored, and transferred using the participant's ID to ensure subject confidentiality. Individuals will not be captured in the photographs; however, if any faces or identifiable characteristics are captured accidentally, these images will be blacked out accordingly.

Double data entry by different study personnel and in-built range/consistency checks will be used to optimize data quality. Discrepancies between data enterers will be flagged by RedCap and adjudicated by the student investigator using hardcopies of the data collection forms.

## **12. Consent Process and Documentation**

Written consent will be obtained from a primary caregiver (typically the mother) for all study procedures (Consent Form A for study procedures; Consent Form B for home audit and photographs of the built environment inside and outside of the home). During the initial home visit, the consent form will be read to the participant's caregiver. If all terms are agreed to, the caregiver can either sign the consent form or thumb stamp it using their left thumb. No data collection procedures will commence until written, informed consent is collected.

The study physician will assess the parent/caregiver's capacity to provide consent. This will be based on the study physician's ample experience working with this particular study population.

## **13. Risks**

This is a minimal risk study. There is a low risk of infection following the collection of hemoglobin concentration via finger prick; appropriate study procedures, including the proper cleaning of the finger using an alcohol swab will help to minimize this risk.

The only potential risk/discomfort associated with wearing the accelerometer and GPS logger is the minimal discomfort and weight of the activity belt. During the daily phone calls, study personnel will ask the caregiver of the participant if there are any problems or concerns with their child wearing the devices. This ensures that if there are any compliance issues surrounding wearing the devices, study personnel will be aware of this immediately. If a participant feels uncomfortable wearing the accelerometer, the study personnel will inform their supervisor, and make appropriate changes to increase compliance and decrease participant burden (e.g., encouraging the participant to wear the belt over/under clothes, depending on preference;

attaching stickers to the devices to make them more visually appealing to children; providing the caregiver with a pedometer to model in front of the child while they wear the activity belt). If after making appropriate changes, the participant still does not feel comfortable wearing the activity belt, they can choose to opt-out of the remainder of the study and still receive compensation, if a minimum of 4 days of accelerometer data collection has been obtained.

If a participant feels uncomfortable wearing the GPS logger specifically, we will allow for the caregiver (or whoever is supervising the child) to carry the device on their person, so long as they are with the child during waking hours. In addition, if the caregiver does not feel comfortable disclosing specific locations that their child visits, they can opt to remove the GPS logger from the pouch attached the activity belt for that specific time period. The device will then be returned to the pouch once the participant has left that specific location.

Research ethics approval will be obtained from both the Research Ethics Board at the Hospital for Sick Children in Toronto and the Research Review Committee and Ethical Review Committee at icddr,b in Dhaka.

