### 1. Study Summary

Title	Risk factors for low physical activity levels in preschool-aged children in a densely populated urban community in Bangladesh
Short Title	Preschooler Physical Activity Study (PresPA Study)
Design	Cross-sectional observational
Study Duration	1 year (August 2017 – August 2018)
Study site	Dhaka, Bangladesh
Primary Objective	To describe the physical activity levels in preschool-aged children in urban Bangladesh.
Primary Outcome	Preschooler physical activity levels (mean activity counts/15 seconds will categorize activity into: light and moderate-to-vigorous physical activity, and sedentary behavior based on predetermined cut-points).
# of Participants	60
Main Inclusion Criteria	
 
• Child is between 34-38 months of age;
 
• Child and primary caregiver reside in Dhaka or urban environs;
 
• Parent/guardian provides written informed consent for study procedures.
 

Main Exclusion Criteria	
 
• Child requires mobility assistance;
 
• Child has been diagnosed with a neurological disorder affecting physical activity (e.g., Cerebral palsy) or a major chronic respiratory or cardiac disease that limits physical activity (e.g., severe asthma, congenital heart disease).
 

Follow-up period	N/A

Main Study Procedures	
 
1. Accelerometry & GPS logging
 
2. Anthropometry
 
3. Blood hemoglobin concentration test
 
4. Home environment audit
 
5. Home perception questionnaires
 
6. Socioeconomic questionnaires
 

-----------------------	---------------------------------------------------------------------------------------------------------------------------------------------------------------------------------------------------------------------------------------------------------------------------------------

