### **9.3.5. Accelerometry & Global Positioning System (GPS) logging (child)**

At the end of the initial home visit, the study personnel will provide the participant with their activity belt. The belt will consist of a tri-axial accelerometer (ActiGraph GT3X-BT, ActiGraph Corp., Pensacola, FL, USA) that will be positioned at the right hip, and a passive GPS logger (iTrail H6000, KJB Security Products Inc., TN, USA) that will be either positioned at the left hip of the child, or on the arm of the caregiver. The placement of the GPS logging device will depend on the participant's comfortability with wearing the device on the activity belt, otherwise it is acceptable for the caregiver to wear it on their person. Both the accelerometer and GPS logger will be charged and initialized prior to the home visit. The study personnel will then provide the caregiver with instructions on how the belt is positioned on the child and explain that the child is to wear the belt 24 hours each day. The belt should only be removed during periods of bathing and swimming. As mentioned above, to improve child comfort during the day or while sleeping, the caregiver may remove the GPS device from the pouch attached to the belt at anytime and wear it on their person (a separate, additional belt will be provided to the

caregiver during the initial home visit), so long as they are with their children at all times during the day. Caregivers can remove the belt while sleeping if they find it uncomfortable, but must reattach it each morning.

The accelerometer will objectively measure all movement of the device-wearer continuously. The device is to be worn continuously for 7 days; however, the child can wear the device for 7 days non-consecutively within a 14-day time period if the caregiver identifies that the child is travelling away from home, is ill (e.g., illness that parent perceives as greatly affecting PA, such as fever, major injury, etc.), bedridden, or hospitalized. Accelerometry and GPS data will not be included in analyses during those specified days. This will continue until the caregiver indicates that the participant has returned home from travelling or is no longer ill, bedridden, or hospitalized, when accelerometry collection can resume. Study personnel will gather this information via the daily telephone calls with the participant's caregiver (section 9.3.6).

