### **9.3.7. Final visit: Home perception questionnaire (caregiver)**

Once the caregiver has indicated that the child has completed their 7 days of wearing the activity belt, study personnel will schedule a clinic visit at the convenience of the participant and their caregiver. If the participant is unable to travel to the clinic, a home visit can be arranged instead. During the final visit, the participant's caregivers will participate in the Home Perception Questionnaire (Form 4) in the form of an interview conducted by study personnel. This questionnaire consists of questions pertaining to the caregiver's perception of the adequacy of facilitating physical activity, safety, and cleanliness inside and outside of the home. This questionnaire will also capture the known physical activity risk factor: screen time . In addition, this questionnaire will collect information on food security, a potential risk factor for low hemoglobin levels, and iron supplement usage. The Home Perception Questionnaire will be conducted during the final visit as opposed to the initial visit in order to avoid influencing the caregiver and effect how the participant wears the activity belt during the accelerometry data collection period.

The caregivers of the participants can opt out of the home perception questionnaire, if they choose to, without penalty.

In addition, child participants within the study will have the opportunity to participate in a general physical checkup during the final clinic visit by our study physician. Participation in the general physical is not mandatory, but is offered as a health incentive to participate in the final visit of the study.

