## **9.6. Sample size and power calculations**

Given 126 screened children, we expect to enroll up to 75 children in the study. For our primary objective, we will need 60 enrolled children with complete accelerometric data to be able to describe the mean counts/15 sec (cp15s) with a margin of error of  $\pm 2.45$  cp15s, assuming a standard deviation of 9.7 cp15s.

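### A pedometer may be handed to some caregivers during accelerometry, and the plan neither lists its use for recording nor handles it in the analysis

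*Combined protocol and SAP*

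**What the plan says.** The Study Summary gives the design as "Cross-sectional observational". Section 10.1 defines the primary measure as "a continuous variable that represents the average total physical activity level of each child", in mean counts per 15 seconds (cp15s) over eligible wear time.

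Section 13 covers poor tolerance of the device: "If a participant feels uncomfortable wearing the accelerometer, the study personnel will inform their supervisor", and staff then "make appropriate changes to increase compliance and decrease participant burden". Three examples follow: wearing the belt over or under clothing, stickers on the devices, and "providing the caregiver with a pedometer to model in front of the child while they wear the activity belt". The pedometer is for the caregiver, and it is used during belt wear.

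Four other places bear on the point:

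- Section 9.3.5: the caregiver has a second belt from the initial visit for carrying the GPS logger ("a separate, additional belt will be provided to the" caregiver). Section 9.3.5 also says that accelerometer data can be seen only once the device is back.
- Section 9.3.6: the daily call covers waking time, belt removal, bedtime and trips away from home.
- Section 9.3.8: haemoglobin is measured after accelerometry so that iron treatment cannot affect activity.
- Section 14: the activity report, which includes average daily steps, is delivered only after the data have been analysed.

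**The concern.** Elsewhere the plan's sequence keeps activity information and treatment away from families until the belt is off. A step counter given to the caregiver partway through does not fit that pattern. It may prompt activity in the caregiver, and a young child may follow.

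Provision would also be selective. Only families whose child dislikes the belt are eligible, so any effect would be tied to tolerance of the measuring device. That could touch the descriptive mean (Objective 1) and also the comparisons between children (Objectives 2 and 3).

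Nothing in the plan would let an analyst find the affected children or days. Pedometer use is not among the listed daily-call items, the covariates in Section 10.3 or the models in Section 10.4.1. The nearest sensitivity analysis, in Section 10.4.2, drops the first day of wear. Section 13 relies on the daily calls to bring discomfort to light, so a pedometer would usually arrive after wear has begun. Dropping day 1 would then tend to remove an unexposed day and keep the exposed ones.

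**Working it through.** **The plan's own figure.** Section 9.6 says "we will need 60 enrolled children with complete accelerometric data" for a margin of ±2.45 cp15s, with SD 9.7. It states no confidence level; 95% is taken from Section 10.4.1, Objective 1.

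- Margin = 1.96 × 9.7 / √60 = 2.454 (2.506 with the t distribution).
- Inverse: (1.96 × 9.7 / 2.45)² = 60.2.

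The stated precision reproduces.

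**Possible effect on the overall mean.** Let *p* be the share of families given a pedometer and *d* the average change in their children's mean cp15s. Neither is in the documents.

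- Bias *b* = *p* × *d*.
- SE = 9.7 / √60 = 1.252.
- Coverage of the nominal 95% interval = Φ(1.96 − *b*/SE) − Φ(−1.96 − *b*/SE).

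| *p* (assumed) | *d*, cp15s (assumed) | Bias, cp15s | Share of 2.45 margin | Coverage |
|---|---|---|---|---|
| 5% | 2 | 0.10 | 4% | 94.9% |
| 10% | 5 | 0.50 | 20% | 93.2% |
| 20% | 5 | 1.00 | 41% | 87.4% |
| 30% | 9.7 (one SD) | 2.91 | 119% | 35.8% |

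**Shift needed for the bias to equal the margin** (*d* = 2.45 / *p*): 49 cp15s at 5%, 24.5 at 10%, 12.25 at 20% and 8.2 at 30%.

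**Partial exposure.** Here *d* applies to a child's whole record. A pedometer issued after a complaint affects only later days. If 5 of 7 equally weighted days followed issue, 20% × 5 would give 1.00 × 5/7 = 0.71 cp15s.

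**Comparisons between children.** If the share of recipients differed between two groups by Δ*p*, the difference in means would shift by Δ*p* × *d*. With assumed shares of 30% and 10% and *d* = 5, that is 0.20 × 5 = 1.0 cp15s.

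**The case against.** The strongest reply is that this is a conditional aid, the last of three examples, intended to help a reluctant child keep the belt on. The caregiver receives it, so any effect on the child's counts is indirect. The text mentions no visible display, step goal or encouragement to walk. All of that stands.

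It is also a fair reply that losing belt-averse children does harm of its own. A child needs at least three valid days of 10 hours (Section 10.1), and the sample target depends on complete records. This stands against simply withdrawing help with compliance. It does not stand against modelling wear with an object that does not count steps.

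A reader might infer more than the documents support, in three ways:

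- **That the mean is biased upward by more than the margin.** With an assumed mean of 150 cp15s, 20% of families and a 10% rise, the shift is 0.20 × 0.10 × 150 = 3.0, above 2.45. All three inputs are assumed. A rise of 15 cp15s in recipients is 15 / 9.7 = 1.5 of the plan's SDs, which is large for an indirect effect. A mean of 150 with SD 9.7 also implies a coefficient of variation of only 6.5%, so the assumed mean and the margin may not belong together. Neither direction nor size is documented.
- **That the pedometer is an activity-feedback device.** This rests on the ordinary meaning of the word; Section 13 does not describe the device.
- **That Section 13 contradicts Section 9.3.7.** The questionnaire is delayed "in order to avoid influencing the caregiver and effect how the participant wears the activity belt during the accelerometry data collection period". That reason concerns how the belt is worn, and the pedometer is meant to support wear. The closer comparison is Section 9.3.8, where influence on activity is the stated reason for the order of procedures.

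**Conclusion.** The point holds as a gap in design and recording. A step-counting device may be introduced during measurement of the primary outcome, only in families whose child tolerates the belt poorly, with no listed record and no analysis that isolates it. The blank log and forms are not reproduced in the document, so a field for this may exist there; the protocol text does not mention one.

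No stated figure is wrong. Under the assumed inputs, the effect on the overall mean runs from negligible (0.10 cp15s) to slightly above the planned margin (2.91 cp15s). The upper end needs about a third of families and a full-SD shift. The effect is probably small unless many families receive a pedometer. The case for acting is that the change is cheap, and that without a record the study could not show the effect to be negligible.

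**What to change.** In Section 13, replace the working pedometer with an aid that shows no step count. The caregiver can model the separate belt already supplied, or a sealed or non-functioning device. Keep the clothing and sticker options.

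If any pedometer has been issued, record the family and the date. Then repeat the Objective 1 to 3 analyses without the days after issue. Objectives 2 and 3 use daily means in a mixed model, so those days can simply be dropped. For Objective 1, recompute the child's mean from the remaining days, and report how many children fall below three valid days as a result.

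The cost is a wording change in the protocol and field instructions, a compliance aid that may appeal less, and one small extra sensitivity analysis if pedometers have been used.
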